**Exposure sessions.** Internet- and smartphone-based interoceptive exposure are well tolerated, acceptable, and effective. We will target AS through graduated exposure to anxiety and distress-provoking situations and response prevention. These exposure exercises were originally created for a previous app-based treatment developed by our team for AS-reduction (e.g., over-breathing, straw breathing, running in place, chair spinning, and head rush). The EASE app will cue the participant to begin the exposure session at the designated time and then the app will guide participants through exposure exercises. Participants will learn to manage negative affect and stress during elevated distress states without acting on acute motivation to suppress distress. In the exercises, the app guides the participant through interoceptive exposures by explaining the activity, normalizing the physical symptoms experienced during the exercise, and relating this experience to the increasing tolerance of physical symptoms (e.g., anxiety, depression), as well as helping to cope with experiences of discrimination. When the participant is ready to begin, the app will assess level of distress (0-100 scale), begin a countdown for a specified amount of time for the

Thoughts		
Tailored treatment messages in real-time	X	

**FULL PROTOCOL TITLE:** Mobile Health to Monitor Risk for COVID-19 and Improve Mental Health during the Pandemic

exposure, and re-assesses level of distress (0-100 scale) once the countdown has expired. This is immediately repeated to ensure habituation to feared sensations. Participants will complete brief questions about the length, engagement, and usefulness of the exposure, and they will be encouraged to continue practicing these exposures daily (i.e., “Practice Stress Management” option on the app home screen). Exposures will incorporate graduated elements to safely elicit strained breathing, racing heart, dizziness, and mild disorientation. These exposures were selected to elicit symptoms that may increase worry about potential COVID-19 infection, particularly among racial/ethnic minority populations.

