*EMAs with tailored real-time treatment messages.* During the 3-month intervention period, a message will be delivered at the end of each EMA (2 per day). When participants provide a pattern of responses that are suggestive of heightened emotional distress (e.g., answering, “neutral, agree, or strongly agree” when asked to rate how much they agree with the statement, “Right now, I feel depressed” using a 5-point Likert scale.), they will be prompted to complete an on-demand exercise (e.g., cognitive restructuring, guided relaxation video). The type of message that is delivered (e.g., coping with depression, coping with anxiety, coping with COVID-19 related anxiety) will be recorded in the database, so we may determine if the message attenuated the targeted symptom (assessed during the next EMA). Maladaptive automatic thoughts will be assessed in EMAs. EMAs will capture participants' beliefs about internal and/or physical sensations experienced. When participants endorse maladaptive cognitive processes, EASE will use response skip patterns to encourage challenging of maladaptive thoughts and to develop more balanced responses. Interactive exercises to guide the participant through the process of challenging dysfunctional thoughts are to be also available ‘on demand.’ Additionally, participants will be instructed to review and practice interoceptive exposure exercises to further normalize symptoms of anxiety and depression as well as consider the uniqueness of these symptoms relative to COVID-19 symptoms.

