*App Configuration.* The mHealth Shared Resource ([name] is the founding director) at the OUHSC and NCI Designated Stephenson Cancer Center (SCC) has developed the Insight™ mHealth Platform which enables researchers to **RAPIDLY** create studies (e.g., most studies are created within 1-2 weeks) that can use EMA and sensor data (i.e., activity monitor) to identify environmental, cognitive, affective, physiological, and behavioral antecedents of health risk behaviors (e.g., smoking, heavy alcohol use, inactivity / obesity) and deliver context-specific adaptive interventions in real-time (see more about Insight™ here: ). The mHealth resource currently employs 11 individuals, including 7 senior programmers (computer scientists/engineers) who develop and maintain our cross-platform Insight™ app and relational databases. To date, the mHealth resource has supported 65 studies including 35 with funding from the NIH. Across studies, thousands of participants have used the Insight™ app. EASE Intervention adherence will be objectively assessed by examining components used by each participant (e.g., videos watched, completed exposure exercises). To access perceived engagement with EASE and control intervention, participants will answer questions about app features used and time, in total, spent using the app each week during the Sunday morning EMA assessment. Similar methods have been used to assess app engagement in past work.

***EMA Types:*** The EMA methodology for this study will be similar to what we have used in our previous studies, and by other researchers. Each EMA will ask about current emotional, physical, and behavioral symptoms, as well as COVID-19 symptoms, and will take approximately two minutes to complete. Two types of EMAs will be used: time-based sampling (i.e., daily diary) and event sampling. Time-based EMAs will be prompted and initiated by the phone two times per day during the 6-month study period (we have had great success with this type of EMA schedule in previous trials, e.g., ~70% EMA compliance over 6 months; see Table 3 for EMA constructs). Also, participants will be instructed to self-initiate event sampling EMAs to record Distress and new COVID-19 symptoms. All EMAs will be date and time stamped for future analyses.

*Time-Based Sampling EMAs:* Daily diary EMAs will be prompted by the smartphone twice per

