*Event Sampling EMAs:* All participants will be asked to initiate "Report Distress" EMAs and answer Core EMA items when they perceive a heightened level of depression and/or anxiety (see Table 3). Participants will be instructed to answer questions based upon immediate thoughts/feelings. EASE participants will receive unique intervention content when they report elevated depression and/or anxiety symptoms. Intervention/coping messages and video content will be different each time the "Report Distress" button is clicked (this component is consistent with 8 of our previous trials on various topics including relapse prevention [e.g., Smart-T, Smart-T Alcohol, Phoenix, MASP, M-ICART] and mood management interventions [e.g., Persist]). Additionally, all participants will be asked to initiate a survey (by clicking the "Report COVID-19 Symptoms" button in the app) if any new COVID-19 symptoms arise between the morning and evening daily diaries. **NOTE:** Our previously developed COVID-19 risk detection algorithm will advise participants to get a test for COVID-19 when elevated risk is detected. The app will immediately trigger an automated and encrypted email to study staff to call the participant and assist with obtaining a COVID-19 test (if desired by the participant).

The EASE app content was created by [name] and [name]. Moreover, all EASE app content in this study will be accessed through the Insight platform, which is owned by the Oklahoma University Health Sciences Center (OUHSC). The EASE app will only be available to research participants.

The control app used in the control condition was created by [name] and [name]. All content found in the control app for this study will be accessed through the Insight platform, which is owned by the Oklahoma University Health Sciences Center (OUHSC). The control app will only be available to research participants.

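### The protocol as supplied names no risk from the EASE-only interoceptive exposures, and no described item asks about acute unwanted effects after an exercise

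*Combined protocol and SAP*

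**What the plan says.** Table 2 (Section 10.0) marks interoceptive exposure for EASE and leaves the control column blank. The control description has videos and reporting buttons but no exposure exercise.

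Under Exposure sessions, the app guides the participant through tasks such as chair spinning, over-breathing and a head-rush exercise. The purpose is explicit: "Exposures will incorporate graduated elements to safely elicit strained breathing, racing heart, dizziness, and mild disorientation". Each exercise is repeated straight away and daily practice is encouraged. The text on tailored EMA messages adds that "participants will be instructed to review and practice interoceptive exposure exercises to further normalize symptoms of anxiety and depression". The same section gives the team's view of tolerability: "Internet- and smartphone-based interoceptive exposure are well tolerated, acceptable, and effective".

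Distress is rated before each exposure, and the app then "re-assesses level of distress (0-100 scale) once the countdown has expired". After that, "Participants will complete brief questions about the length, engagement, and usefulness of the exposure".

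Section 12.0 describes the study as minimal risk. It names a confidentiality breach, a data-security failure, discomfort at being questioned, and the time burden. It commits the team to monitoring the listed risks and reporting adverse events to the IRB. It also says that a protocol exists for severe symptoms, of which the visible step is referral to mental health providers. It does not mention the exposures.

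Follow-up assessments and Table 3 list the 3- and 6-month battery. No measure there is described as asking about unwanted effects.

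**The concern.** Brief dizziness or a racing heart is the intended stimulus, so those sensations are not the issue. The issue is an effect beyond the intended one: a fall, a faint, or symptoms that are severe or do not settle. These can follow from spinning or over-breathing with nobody present, and only one arm is asked to do the exercises.

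The duty to report adverse events works only if staff learn of them. If no item asks, reports depend on who volunteers them. A count of zero would then have no known number of people asked behind it, and it could not support a statement about how well EASE was tolerated. With no identical question in the two arms, harms could not be described side by side on the same footing.

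**Working it through.** **Step 1. Would any described route record an acute event after an exposure?** All routes are from Section 10.0 unless marked.

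| Route | Arm | What it is described as asking | Asks about a fall, faint, or severe or prolonged symptoms after an exercise? |
|---|---|---|---|
| Distress rating, 0-100, before and after | EASE | Distress level | No |
| Post-exposure questions | EASE | Length, engagement, usefulness | No |
| Twice-daily EMAs | Both | "Each EMA will ask about current emotional, physical, and behavioral symptoms, as well as COVID-19 symptoms" | Not linked to an exercise |
| Report Distress | Both, self-started | Participants are to "answer Core EMA items when they perceive a heightened level of depression and/or anxiety"; Table 3 lists affect, location, pain and coping | No |
| Sunday EMA | Both | Includes OASIS, ODSIS, SSASI, app quality | No; tracks status |
| 3- and 6-month OASIS, ODSIS, PHQ-4, PEG, HRQOL | Both | Symptom, pain and health status | No; would show sustained worsening |
| Self-Rated Health; Additional Aim 1 Measures (4 items) | Both | Item wording not shown | Cannot be determined |
| Call Staff button | Both | Nothing; the participant must call | Not solicited |
| Interviews | Selected participants, both arms | App utility and improvement | Not described |
| Section 12.0 reporting and referral | Both | Acts once an event is known | Not solicited |

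The repeated scales are the same in both arms and would reveal lasting deterioration. What is left without a described question is mainly the acute physical event.

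**Step 2. What would asking buy?** The protocol gives no event rate or safety figure, so there is nothing to reproduce. Inputs: 440 in the intervention group (Section 5.0) and 80-90% retention (Section 8.0), giving 0.80 × 440 = 352 and 0.90 × 440 = 396. With no events among n people who performed exposures and were asked, the exact one-sided 95% upper bound is 1 − 0.05^(1/n):

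- n = 440: 0.68%
- n = 396: 0.75%
- n = 352: 0.85%

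Section 1.0 gives 420 for the EASE arm instead; the bound is then 0.71%.

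These values assume that everyone counted performed an exposure. The protocol gives no uptake figure. If only half did (an assumption for illustration), n = 440/2 = 220 gives 1.35% and n = 352/2 = 176 gives 1.69%.

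The chance of at least one event is 1 − (1 − p)^n. For assumed true rates p of 0.2%, 0.5% and 1%, it is 59%, 89% and 99% with n = 440, and 51%, 83% and 97% with n = 352.

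**Step 3. Could the interviews stand in?** The quota is 20-30 per racial/ethnic group. With four groups, that is 80-120 EASE participants if it applies within each condition: 80/440 = 18% to 120/440 = 27%. If it is split evenly across both conditions, it is 40-60, or 9% to 14%. Either way most of the arm is not interviewed, and the stated topic is not harm.

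**The case against.** The strongest reply is that the ascertainment may sit elsewhere. Section 7.0 places the full monitoring plan in the grant, Section 12.0 refers to a developed severe-symptom protocol, and Section 18.0 refers to a separately uploaded consent form. None is in view. The Additional Aim 1 Measures are never described, and the Self-Rated Health wording is not shown. This stands, and it limits the point to the document supplied.

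Second, repeated anxiety, depression and pain measures would show sustained harm by arm. This also stands and narrows the gap to acute events.

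Third, the protocol calls such exposures well tolerated and says they were created for an earlier app by the same team. That supports the minimal-risk judgement, but it does not count events in this trial.

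Fourth, a recall question at 3 or 6 months is a weak instrument for a brief event and adds to a battery that Table 3 totals at 188 items. This is fair, and it is why the post-exposure item carries most of the value.

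A reader might infer more than the text supports:

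- **That the trial collects no harms data.** The general reporting duty and the unseen plans rule this inference out.
- **That the analysis overview in Section 20.0 shows that no harms table is planned.** It introduces models for the aims and points to later sections that are not in the supplied text, so its silence is weak evidence.
- **That the minimal-risk classification is wrong.** Nothing here shows that.

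**Conclusion.** The point holds for the protocol as supplied. Section 12.0 omits any risk from the one physically provocative component, which only EASE receives, and no described item asks about acute unwanted effects after an exercise.

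It is minor. It concerns what is recorded about safety, and no efficacy estimate changes. The upper bound of 0.68% to 0.85% is the best case with zero events, reached only if all 440 to 352 participants performed exposures and were asked. Lower uptake widens it. The true event rate is unknown, and the unseen documents may already close the gap.

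**What to change.** 1. In Section 12.0, name falls, fainting, and severe or prolonged symptoms or distress as foreseeable exposure risks. State that the brief intended sensations are not adverse events. Check that the consent form agrees.
2. Add one unwanted-effects item to the questions already asked after each exposure. Use participants who completed exposures as the denominator; the App Configuration text says completed exercises will be examined for adherence, so the record should exist.
3. Ask one identical adverse-event question in both arms at 3 and 6 months and tabulate the answers descriptively by arm.
4. If the grant's monitoring plan already does this, replace items 2 and 3 with a cross-reference.

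Base any zero-event bound on the number who performed exposures. How a reported event is handled clinically is for the investigators to set. The cost is a few lines of risk text, two app items, slight participant burden and an IRB amendment.

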### **Follow-up assessments:**

Following completion of the baseline assessment, the app will automatically begin prompting twice daily EMAs for 6-months. Participants will complete two scheduled daily ecological momentary assessments (EMAs) during the intervention and continued assessment periods that will guide a just-in-time approach to immediate, personalized behavioral health care (please see EMA types section below). *Assessments will be completed remotely and no in-person study visits will be required.*

Moreover, Participants will complete follow-up assessments at 3- and 6-month post-baseline (i.e., end-of-treatment and end of 3-month continued monitoring period) using the InsightTM app. These assessments will include a qualitative interview for selected participants. The follow-up surveys will be distinguishable from EMAs (i.e., a new “Follow-up” button will appear on the app home screen (both groups) 3- and 6-month post-baseline and participants will click this button to initiate the assessment). Participants will receive a daily alert from the app to click the “Follow-up” button until the assessment is completed. Like the baseline, the follow-up assessments will include the PSS-4, PHQ-4, HRQOL, F-SozU K-6, MSSS, Covid-19 Vaccine Hesitancy Survey, Additional Aim 1 Measures, FSQ, BRFSS, Frequency of Attendance at Religious Services, Discrimination Burden, SRH, Employment Status, COVID-19 Psychological Impact Survey, Daily Activities, Change in Fast Food Consumption, Three-item Loneliness Scale, COVID-19 Substance Use, AUDIT-C, Marijuana/Cannabis Use Behavior, EDS, CRBS, SDS, PEG Scale, SSASI, OASIS, ODSIS, and Fear of COVID-19 (see above for description of measures). Additionally, the 10-item System Usability Scale will be incorporated to assess perceptions of the usability of the apps (i.e., intervention and control). Lastly, the 6-month follow-up assessment only will include two demographic questions taken from the Demographic/Background Information Questionnaire.

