app from the research team. The control app was built using the Insight platform. Participants assigned to the control app will have access to: 1) a series of educational videos that discuss meditation techniques, mindfulness exercises, and stress reduction exercises, 2) a feature that allows participants to report when they are experiencing heightened stress, anxiety or depression, and 3) a “Report COVID-19 Symptoms” button that allows participants to report any COVID-19 symptoms they are experiencing to research staff at any time throughout the study. If a symptom cluster consistent with COVID-19 is detected, an encrypted email will be sent to the research team and they will work with the participant to help them find a local testing center. Instructions on how to use the app will be available to participants on the home screen, and will accessible at all times. Additionally, participants will be able to call study staff by pressing the “Call Staff” button on the study home screen. Participants will receive 2 daily EMAs during which they will be prompted to watch aforementioned educational videos twice per week. Following the intervention period, participants will be encouraged to continue to practice the meditation, mindfulness, and stress reduction techniques they have learned, report moments of heightened stress, depression, or anxiety, and report any COVID-19 symptoms they experience.

**Ecological Momentary Assessments (EMA).** EMAs are currently the most accurate way to measure phenomena in real-time, natural settings. EMA items will identify fluctuations in key variables that predict study outcomes with less bias than traditional in-person assessments. EMA data will be used to identify moments of distress (e.g., anxiety/depression), tailor EASE treatment, and identify treatment mechanisms.

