Data analysis overview: Hypotheses for Aims 1 and 2 will be examined using latent growth models (LGM), multilevel structural equation models (MSEM) and latent difference score models using MPlus 8.0. To simplify subsequent sections, an overview of the common data analysis elements is presented first. Data will first be examined for multivariate normality and outliers to determine the most appropriate estimator. The maximum likelihood (ML) estimator will be used if data are approximately normal. Robust maximum likelihood (MLR) will be used if the data are not multivariate normal. We anticipate some participant attrition during the trial. Missing data will be handled in all analyses using direct ML techniques within MPlus under a missing at random (MAR) assumption. Modern missing data techniques such as direct ML increase statistical power and provide more accurate estimates of model parameters and standard errors and are the recommended intent-to-treat approach for clinical trials. LGM will generally be used to model outcomes collected at major assessments. MSEM will be used to further examine the longitudinal course of outcomes and hypothesized mechanisms of action as MSEM is ideally suited for disentangling within and between individual variance in order to more precisely estimate main effects, lagged effects, and indirect effects in intensive longitudinal designs. Evaluation of model fit in the LGM/MSEM models will be examined using fit diagnostics (i.e., standardized residuals) and common fit statistics (i.e., root mean square error of approximation) following the associated cutoff criteria recommended by Hu & Bentler. We will assess the equivalence of the treatment groups on key baseline

**FULL PROTOCOL TITLE:** Mobile Health to Monitor Risk for COVID-19 and Improve Mental Health during the Pandemic

variables (demographics and psychological variables); variables on which the groups differ will be used as covariates in the final analyses. We will also examine attrition from the study as a dichotomous outcome and use logistic regression to determine if treatment assignment predicts attrition.

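### Does the plan need to fix the contrast for deciding whether a tailored message eased the symptom at the next EMA?

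*Combined protocol and SAP*

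**What the plan says.** Section 10.0, in the paragraph on EMAs with tailored real-time messages, states: "During the 3-month intervention period, a message will be delivered at the end of each EMA (2 per day" and so on for the EASE app. It then adds a second layer: "When participants provide a pattern of responses that are suggestive of heightened emotional distress", the participant is prompted to do an on-demand exercise. The worked example of a trigger is a rating of neutral or above on a five-point depression item. The message type is stored "so we may determine if the message attenuated the targeted symptom (assessed during the next EMA" in the protocol's words. Table 2 marks the row "Tailored treatment messages in real-time" for EASE only, while control participants also answer two EMAs a day.

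Two other places in Section 10.0 bear on this. Under Ecological Momentary Assessments: "EMA data will be used to identify moments of distress (e.g., anxiety/depression), tailor EASE treatment, and identify treatment mechanisms". Under Follow-up assessments, the EMAs are described as running "during the intervention and continued assessment periods that will guide a just-in-time approach to immediate, personalized behavioral health care", so months 4 to 6 cannot be assumed free of messages.

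The analysis text is the overview in Section 20.0. It names latent growth models, multilevel structural equation models (MSEM) and latent difference score models for Aims 1 and 2, and says "MSEM is ideally suited for disentangling within and between individual variance in order to more precisely estimate main effects, lagged effects, and indirect effects". It mentions no message term, no comparator for messages and no conditioning on the rating that caused a prompt.

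**The concern.** The exposure here is decided by an earlier value of the outcome: participants are prompted because they have just rated a symptom high. A high rating tends to be followed by a lower one whatever the app does, so a simple before-and-after comparison would credit the message with regression to the mean. Comparing the next rating after triggered and untriggered EMAs errs the other way, because prompts go to moments that were already worse and distress persists. Both analyses are compatible with the wording in Section 10.0, and with a message that does nothing they give opposite signs.

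There is also a question of what is being compared. Since every scheduled EASE EMA in the intervention period ends with a message, a within-EASE contrast cannot be message against no message. It is a triggered exercise prompt against whatever message follows an EMA without a trigger. With EMA data described as a source of evidence on treatment mechanisms, a result of the wrong sign could be published as a mechanism finding.

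**Working it through.** The protocol gives no effect size, SD or power for this analysis, so there is no figure to reproduce. The check asks how far the answer moves with the contrast, and then whether the named methods can deal with it.

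**Inputs from the protocol.** 440 per arm (Section 5.0; the 420 in Section 1.0 makes no difference here). Two EMAs a day for 30 days is 60 a month (Section 15.0), so 3 × 60 = 180 over the intervention period. About 70% answered (Section 10.0, EMA Types: "we have had great success with this type of EMA schedule in previous trials, e.g., ~70% EMA compliance over 6 months"), so 0.70 × 180 = 126 per participant. Trigger: a rating of 3, 4 or 5 on a 1–5 item (the example in Section 10.0).

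**Assumed.** Between-person share of variance (ICC) 0.3, 0.5 or 0.7; within-person lag-1 autocorrelation ρ of 0, 0.3 or 0.6; about half of EMAs at trigger level; EMAs missed at random. That is nine settings, five replicates each.

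**Mechanism.** On the latent scale the correlation between consecutive EMAs is r = ICC + (1 − ICC)ρ. It runs from 0.3 + 0.7 × 0 = 0.30 to 0.7 + 0.3 × 0.6 = 0.88. With no message effect, the expected change from a moment d above the mean is −(1 − r)d, a fall, while the expected next value is still rd above the mean. One quantity produces both signs.

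**Results with a true effect of zero** (points on the item):

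| Contrast | Range over nine settings |
|---|---|
| (a) Change from a trigger-level EASE EMA to the next | −0.18 to −0.76 |
| (b) Next rating, triggered minus untriggered, unadjusted | +0.53 to +1.67 |
| (c) Change, triggered minus untriggered | −0.36 to −1.50 |
| (d) EASE minus control at the same triggering rating | about 0 (0.000 to −0.007) |

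**Arithmetic check at ICC 0.3, ρ 0.** The trigger share is 0.497, (a) is −0.756, (b) is 0.534 and (c) is −1.499. Change after untriggered EMAs is therefore −0.756 + 1.499 = +0.743. Averaged over all EASE EMAs: 0.497 × (−0.756) + 0.503 × 0.743 = −0.376 + 0.374 = −0.002. The fall in (a) comes entirely from selecting high ratings. The triggered-minus-untriggered gap at the current EMA is (b) − (c) = 0.534 + 1.499 = 2.033, so the 0.534 at the next EMA is what remains of a gap that existed before any prompt.

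**With a latent effect of −0.2 SD,** contrast (d) gives −0.11 to −0.22, the right direction. Contrast (b) still shows a rise, 0.27 to 1.41.

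**Lagged regression within EASE.** A second simulation used item means of 2.0, 2.5 and 3.0, SD 1.1, between-person share 0.4 or 0.6 and autocorrelation 0.2 or 0.5 (12 settings). With zero effect, the prompt coefficient is +0.21 to +0.69 without the triggering rating (person fixed effects) and −0.04 to +0.03 with it (over three ways of handling the person term). A true fall of 0.15 is read as a fall of 0.12 to 0.19 with the rating, but as a rise of 0.07 to 0.53 without it. Where ratings pile up at the floor, the adjusted null estimate runs from −0.03 to +0.10, and a true 0.15 can read as little as 0.04.

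**What the named methods allow.** A lagged MSEM can carry the previous rating as a predictor, and a latent difference score model can let change depend on prior level. Either makes room for the one covariate that matters, using data already collected. Control EMAs at the same rating are also in the database.

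**The case for a change.** The best argument for a change is that two defensible-looking analyses disagree in sign, that only conditioning on the triggering rating brings them near the truth, and that saying so in advance would cost a sentence or two. Naming a model family does not settle it, since a lagged prompt effect can be fitted in MSEM with or without that rating. All of this is correct as statistics, and the two opposite signs appeared in every null setting of the first simulation.

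What it does not show is an error in the plan. No before-and-after test, and no unadjusted lagged effect, is stated anywhere. The clause sits in a description of app features and says what a stored field may be used for. The mechanisms that Aim 2 and H3 name are anxiety sensitivity and COVID-19 stress and fear, not single messages. The overview in Section 20.0 also announces later sections that are not in the text available, so silence there is weak evidence about what was intended.

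Nor is an obvious sentence waiting to be added. A model with one prompt indicator would ignore the message type and targeted symptom, which are the reason for the log. Under a single-item trigger, triggered and untriggered EASE EMAs share no rating, so a within-EASE estimate relies on an assumed straight line. Control EMAs at the same rating supply the overlap, but they are selected after randomisation and the arms differ in other content. Neither contrast separates the message from on-demand material used before the next EMA.

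**Conclusion.** No change is needed. The gap is real but belongs to an optional exploratory use of the EMA log. The randomised comparison and H1 to H4 are unaffected, and the methods already named can include the triggering rating, as an experienced analyst would.

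A naive choice could cost a spurious fall of roughly 0.2 to 0.8 points or, with unadjusted group means, a spurious rise of roughly 0.5 to 1.7. With the triggering rating included, or with control EMAs matched on it, the error under the null is mostly within a few hundredths of a point and at worst about 0.1 when ratings sit near the floor. The directions follow from the trigger rule together with any correlation between consecutive ratings that is positive but short of perfect. The sizes depend on assumed means, SDs, between-person share, autocorrelation and random non-response, and should be read as orders of magnitude. Even a well-adjusted result would remain exploratory.
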